12.0 Descriptive Factors

12.1 International Prognostic Index (IPI) [Shipp et al, 1993]: low risk (0 or 1 risk factors) vs. low intermediate (2 risk factors) vs. high intermediate (3 risk factors) vs. high (4 or 5 risk factors)

Risk Factors	0 points	1 point
Age	≤ 60 yrs.	> 60 yrs.
Serum LDH	≤ 1 x normal	> 1 x normal
ECOG PS	0 or 1	≥2
Stage	I or II	III or IV
Extranodal involvement	≤1 site	>1 site

Total number of risk factors = sum of the number of points for each prognostic factor.

Mantle Cell Lymphoma International Prognostic Index (Formula-based MIPI): Scores determine risk group: Low risk (<5.7) vs. Intermediate risk (≥5.7-<6.2) vs. High risk (≥6.2).

The MIPI score is calculated by this formula: $[0.03535 \times \text{age (years)}] + 0.6978$ (if ECOG > 1)+ $[1.367 \times \log_{10}(\text{LDH/ULN})]$ + $[0.9393 \times \log_{10}(\text{WBC count per }\mu\text{L})]$.

Note: The MIPI score will be calculated in Rave once the components are entered.

13.0 Treatment/Follow-up Decision at Evaluation of Patient

- Patients who achieve a CR or PR at EOI will receive post induction maintenance treatment with rituximab and hyaluronidase human + venetoclax for up to one year (see Section 7.0).
- 13.2 Patients who complete post-induction maintenance treatment will continue to clinical

- follow-up, every 90 days (3 months) +/- 14 days for 2 years.
- 13.3 Patients who complete 2 years of clinical follow-up will continue to survival follow up for a maximum of 5 years from registration.
- 13.4 Patients who go off treatment for adverse events will proceed to clinical follow up.
- Patients who receive alternative therapy or develop progression by CT-based criteria or by PET-CT based criteria at any time while receiving therapy or while in clinical follow-up will go to survival follow up.
- 13.6 Patients who go off protocol treatment for reasons other than progression or alternative therapy will go to clinical follow-up.
- **13.7** Additional reasons for study treatment discontinuation.
 - 13.71 Patients will go to survival follow-up if pregnancy occurs.
 - 13.72 If a patient develops any medical condition that the investigator determines may jeopardize the patient's safety if they continue to receive study treatment they will be removed from treatment and continue to clinical follow up.
- **13.8** Reasons for patient discontinuation from study. No further follow up of any kind will be required.
 - 13.81 Patient withdrawal of consent for all follow-up
 - 13.82 Study termination or site closure
 - 13.83 Patient non-compliance, defined as failure to comply with protocol requirements as determined by the investigator
- 13.9a A patient is deemed *ineligible* if after registration, it is determined that at the time of registration, the patient did not satisfy each and every eligibility criteria for study entry. The patient may continue treatment off-protocol at the discretion of the physician as long as there are no safety concerns, and the patient was properly registered. The patient will go directly to the event-monitoring phase of the study (or off study, if applicable).
 - If the patient received treatment, all data up until the point of confirmation of ineligibility must be submitted. Survival follow-up will be required per Section 18.0 of the protocol.
 - If the patient never received treatment, on-study material and the off-treatment form must be submitted. No further data submission is necessary.
- 13.9b A patient is deemed a *major violation*, if protocol requirements regarding treatment in cycle 1 of the initial therapy are severely violated that evaluability for primary end point is questionable. All data up until the point of confirmation of a major violation must be submitted. The patient will go directly to the survival follow-up phase of the study. The patient may continue treatment off-protocol at the discretion of the physician as long as there are no safety concerns, and the patient was properly registered. Survival follow-up will be required per Section 18.0 of the protocol.

13.9c A patient is deemed a *cancel* if he/she is removed from the study for any reason before any study treatment is given. On-study material and the Off Treatment Form must be submitted. No further data submission is necessary.

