22 ACCRU LY-1806

4.0 Test Schedule

	Days Prior to Registration			Induction (21-day cycles)			EOI ¹	Maintenance (12 months)	EOM ²	Post- Treatment	
Tests and Procedures	≤ 30	≤ 14		ycle ±1 d		Cycle 2 (±2 d)	Cycles 3-6 (±2 d)	After last induction	Monthly (30days)	35 days after last dose	clinical follow- up period (q3m for 2 years
	days	days	D1	D8	D15	D1	D1	dose	(±1 week) D1	(±14 days)	+/- 14 days)
Complete Medical history	X										
ECOG Performance Status	X		X	X	X	X	X	X	X	X	X
Physical exam, weight and vital signs (blood pressure, pulse, O2) ⁴	X		X	X	X	X	X	X	X	X	X
Height	X										
12-lead EKG ⁸	X										
MUGA/echocardiogram ⁸	X										
Hematology (CBC and diff)		X	X16	X	X	weekly ¹⁸	X	X	X	X	
Chemistry Labs ⁷		X	X 16	X	X	X	X	X	X	X	
Coagulation (INR, aPTT [or PTT], and PT)		X									
Serum Pregnancy test ³		X^3	X^3			X^3	X ³	X	X^3	X^3	
HIV ¹⁴ , HBV ¹³ , HCV ⁶	X										
Quantitative IgA, IgG, IgM			X					X		X	X
Optional Whole blood for MRD ¹⁷			X					X		X	
Optional Immunology Research Blood ^{12 R}			X ¹²				X ¹²	X^{12}	X ¹²		X ¹²

	Days Prior to Registration			Induction (21-day cycles) EOI ¹		Maintenance (12 months)	EOM ²	Post- Treatment clinical follow-			
Tests and Procedures	≤ 30	≤ 14	l	Cycle 1 (±1 d)		Cycle 2 (±2 d)	Cycles 3-6 (±2 d)	After last induction	(Soddys)	35 days after last dose	
	days	days	D1	D8	D15	D1	D1	dose	(±1 week) D1	(±14 days)	+/- 14 days)
Review Patient Medication Diary ¹⁵				X	X	X	X	X	X		
Optional tissue specimen R			X ¹¹					X^{11}			
Mandatory tissue specimen 19 R	X										
Concomitant medications	X					To be	recorded conti	inually until er	nd of treatment		
Adverse Event Assessment ⁵	X					To be assessed	d continually				
PET-CT scan	X							X	X ⁹	X	X ⁹
Bone marrow biopsy and aspirate	X^{10}							X^{10}			

¹ End of induction (EOI) is between 28-42 days after the last induction dose of rituximab and hyaluronidase human and polatuzumab vedotin.

² End of maintenance (EOM) visit may take place at 35 days +/- 14 days from the last dose of venetoclax treatment.

³ For women of childbearing potential only. Must be done ≤7 days prior to registration, D1 of each induction cycle, Day 1 of each maintenance cycle, and end of maintenance. Test done ≤7 days prior to cycle1 day 1 can serve as cycle 1 day 1 test.

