4.1 Survival Follow-up

	Survival Follow-up Phase ¹							
	Every 90 days until subsequent treatment or PD ² After subsequent treatment or PD ² q. 180 days Death New Primar							
Survival Follow Up	X	X	X	X	At each occurrence			

¹ If a patient is still alive 5 years after registration and they have completed protocol therapy, no further follow-up is required.

⁸ Patients with known cardiac dysfunction are required to have EKGs and assessments of left ventricular ejection fraction at screening and as clinically indicated afterwards.

⁹ PET/CT in maintenance and post treatment every 6 months or per standard of care.

¹⁰ Baseline bone marrow biopsy and aspirate can be collected within 90 days of registration if negative. However, if bone marrow is positive after most recent therapy (even if greater than 90 days prior to registration), bone marrow biopsy and aspirate does not need to be repeated, but must be recorded as positive on the pre-treatment staging. Repeat Bone Marrow biopsy only in patients who are bone marrow positive at baseline and a CR at EOI to confirm EOI CR. Repeat Bone Marrow biopsy not needed in maintenance.

¹¹ Tissue specimen optional at the end of cycle 1 and optional at the time of progression. See Section 17.0 for additional details.

¹² Draw at baseline (drawn after registration but prior to cycle 1 treatment), day 1 of cycle 3, day 1 of cycle 7, day 1 of final maintenance cycle, and one year after completion of maintenance if patient is a CR. See Section 14.0 for further details.

¹³ Screen all patients for hepatitis B (HBV) infection before initiating treatment with Rituxan. For patients who show evidence of prior hepatitis infection, consult an expert in managing hepatitis B regarding monitoring and consideration for HBV antiviral therapy before and/or during Rituxan treatment (see Section 9.5).

¹⁴ If HIV testing is done \leq 180 days prior to registration it does not need to be repeated.

¹⁵ Patients will be required to keep a medication diary for venetoclax using the diary in Appendix V. Sites will be required to upload medication diary to RAVE at the end of each cycle.

¹⁶ Hematology and chemistry will be obtained prior to administering venetoclax (predose) and 8 and 24 hours after the first dose only. Laboratory samples should be sent and analyzed immediately.

¹⁷ MRD Testing to be completed at Mayo Clinic Rochester for patients who consent to optional collection.

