16.2 Statistical Design

- 16.21 Decision Rule: The largest success proportion where the proposed treatment regimen would be considered ineffective in this population is 15%, and the smallest success proportion that would warrant subsequent studies with the proposed regimen in this patient population is 35%. The following one-stage design with an interim analysis is based on a two-stage Simon optimum design² and requires 46 evaluable patients to test the null hypothesis that the true success proportion in this patient population is at most 15%.
 - 16.211 Interim Analysis: Enter 16 evaluable patients into the study. If 3 or fewer successes are observed in the first 16 evaluable patients, we will consider this regimen ineffective in this patient population and terminate the study. Otherwise, if the number of successes is at least 4, we will continue accrual.
 - 16.212 Final Decision Rule: Enter an additional 30 evaluable patients into the study. If 10 or fewer successes are observed in the first 46 evaluable patients, we will consider this regimen ineffective in this patient population and terminate the study. Otherwise, if the number of success is at least 11, this will be considered evidence of promising activity and the treatment may be recommended for further testing in subsequent studies in this population.
 - 16.213 Over Accrual: If more than the target number of patients are accrued, the additional patients will not be used to evaluate the stopping rule or used in any decision-making process. Analysis involving over accrued patients is discussed in section 16.313.

NOTE: We will not suspend accrual at the interim analysis to allow the first 16 patients to become evaluable, unless undue toxicity is observed. Given the limited overall sample size and the inclusion of an AE stopping rule, we feel it is ethical to not halt accrual for the interim analysis. However, if accrual is extremely rapid, we may temporarily suspend accrual in order to obtain safety data on these patients before reopening accrual to further patients.

- 16.214 Dose de-escalation in safety analysis: A safety analysis will be performed in the first 6 evaluable patients per Section 16.4. In the case of unacceptable toxicity, the dose will be de-escalated. If this occurs, the first 6 patients will be evaluated separately and will not be included in any decision-making criteria.

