16.31 Primary Outcome Analysis

- 16.311 Definition: The primary endpoint of this trial is the complete response rate at the end of induction as determined by investigator on the basis of PET-CT scans according to Lugano 2014. A complete response is defined as an objective status of CR at the end of induction. All patients meeting the eligibility criteria who have signed a consent form and have begun treatment will be evaluable for response, unless they are determined to be a major violation. Only MCL patients treated at the final dose level will be included when evaluating the decision rules in Sections 16.211 and 16.212. Patients without MCL and patients treated at other dose levels will be summarized separately.
- 16.312 Estimation: The proportion of success will be estimated by the number of success divided by the total number of evaluable patients. 95% confidence intervals for the true success proportion will be calculated according to the approach of Duffy and Santner³.
- 16.313 Over Accrual: If more than the target number of patients are accrued, the additional patients will not be used to evaluate the stopping rule or used in any decision-making process; however, they will be included in final point estimates and confidence intervals.

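### Section 13.83 ends all required follow-up for investigator-judged non-compliance, against 13.6, so evaluable patients can lose later PFS and OS data; whether early stoppers have the EOI scan also needs stating

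*Combined protocol and SAP*

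**What the plan says.** **Follow-up after stopping.** Section 13.4: "Patients who go off treatment for adverse events will proceed to clinical follow up". Section 8.2 agrees and adds that such patients stay in the study. Section 13.6: "Patients who go off protocol treatment for reasons other than progression or alternative therapy will go to clinical follow-up". Section 13.8 then opens a separate list: "Reasons for patient discontinuation from study. No further follow up of any kind will be required". Its three entries are withdrawal of consent for follow-up (13.81), study or site closure (13.82) and non-compliance as judged by the investigator (13.83). Treated ineligible patients (13.9a) and major violations (13.9b) go to survival follow-up.

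**The endpoints affected.** Sections 16.323 and 16.324 define PFS and OS from registration, estimate them by Kaplan-Meier and compare them by ibrutinib exposure with log-rank tests. Neither states a censoring rule.

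**EOI imaging.** Section 16.311 sets the primary denominator: "All patients meeting the eligibility criteria who have signed a consent form and have begun treatment will be evaluable for response", apart from major violations. Success is CR at EOI, and the test schedule has no PET-CT between baseline and EOI. Footnote 1 of the schedule: "End of induction (EOI) is between 28-42 days after the last induction dose of rituximab and hyaluronidase human and polatuzumab vedotin". Footnote 9: "PET/CT in maintenance and post treatment every 6 months or per standard of care". Section 7.2 places the EOI response after induction is completed, the blood table in 14.1 equates EOI with day 1 of cycle 7, and 16.328 also uses cycle 7.

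**The concern.** Non-compliance is not withdrawal of consent. A patient who misses visits or tablets can still be known to be alive or dead, and survival status needs no compliance with treatment. Under 13.83 the investigator's judgement alone releases the site from collecting it. Missed visits and tablets may go together with toxicity or decline. If they do, censoring these patients is informative, and Kaplan-Meier and log-rank methods assume that it is not. The trial is small and PFS and OS are compared between two subgroups, so a few such patients matter.

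The second matter concerns the primary endpoint. It rests on one scan, and an early stopper stays in the denominator. If sites differ on whether that patient has an EOI scan, CRs will be assessed at different times or not at all.

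**Working it through.** **1. The follow-up rules side by side.**

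| Patient | Section | Follow-up required | In the primary denominator (16.311)? |
|---|---|---|---|
| Stops for an adverse event | 13.4, 8.2 | Clinical follow-up | Yes |
| Stops for any cause except progression or other therapy | 13.6 | Clinical follow-up | Yes |
| Treated, later found ineligible | 13.9a | Survival follow-up | No |
| Major violation in cycle 1 | 13.9b | Survival follow-up | No |
| Judged non-compliant | 13.83 | None | Yes, unless a major violation |

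A patient taken off treatment for non-compliance meets the terms of 13.6 and of 13.83, which give opposite instructions. The table also shows a reversed order: two groups outside the primary analysis keep survival follow-up, and one inside it does not.

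**2. Size for PFS and OS.** The documents give no rate of non-compliance, so the number lost, m, is an assumption. If m patients of N are lost before a landmark time and the rest are followed to it, the event-free proportion at that time is known only to within m/N (all lost had the event, or none did). N = 46 is from 16.22. N = 25 is the minimum number of ibrutinib-naïve patients in section 5.3, out of 46 + 5 = 51 accrued.

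| m (assumed) | m/46 | m/25 |
|---|---|---|
| 1 | 2.2% | 4.0% |
| 2 | 4.3% | 8.0% |
| 5 | 10.9% | 20.0% |

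**3. When an early stopper would be scanned.** Take a patient whose last infusion is on day 1 of cycle 2, which is day 1 + 21 = 22. Footnote 1 puts EOI at day 22 + 28 = 50 to 22 + 42 = 64. A patient who completes six cycles has the last infusion on day 1 + 5 × 21 = 106, and EOI on days 134 to 148. If EOI instead means cycle 7 or completed induction, the early stopper has no EOI date, and the next imaging rule is footnote 9.

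**4. The plan's own power figures.** Inputs from 16.21: stop if at most 3 CRs in 16; promising if at least 11 in 46; null rate 15%, target 35%. With X ~ Bin(16, p) and Y ~ Bin(30, p),

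P(promising) = Σ over x = 4 to 16 of P(X = x) × P(Y ≥ 11 − x); P(interim stop) = P(X ≤ 3).

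This gives 0.0486 at 15% and 0.8506 at 35%, with interim stopping 0.7899 and 0.1339. The table in 16.24 (0.049, 0.851, 0.790, 0.134) is reproduced.

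**5. Illustration for unscanned patients.** Assume that a share d of evaluable patients has no EOI scan, independently of response, and counts as non-CR. Then p becomes p(1 − d).

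| d (assumed) | 0.35(1 − d) | Power | Interim stop at 35% | Type I error |
|---|---|---|---|---|
| 0 | 0.3500 | 0.851 | 0.134 | 0.0486 |
| 5% | 0.3325 | 0.807 | 0.168 | 0.0356 |
| 10% | 0.3150 | 0.754 | 0.207 | 0.0253 |
| 20% | 0.2800 | 0.615 | 0.304 | 0.0115 |

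If unscanned patients were dropped and replaced instead, and all were true non-CRs, the null rate among those assessed at d = 10% would be 0.15/0.90 = 0.167 and the type I error 0.088. The denominator in 16.311 does not allow this, but no sentence states that an unassessed EOI counts as non-CR.

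**The case against.** **On non-compliance.** Section 13.6 is about leaving treatment and 13.8 about leaving the study, so they can be read as different events. Section 13.8 also says that follow-up is not required; it does not forbid it. No document shows that non-compliance tracks toxicity or decline, and 2.2% is the weight of one patient, not a frequency. All of that is fair. But nothing tells a site which rule governs a patient to whom both apply, sites can be expected to collect what is required, and no reason is given for treating these patients less fully than major violations.

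**On early stoppers.** A reader might infer from 13.4 and 13.6 that early stoppers have no EOI scan. The documents do not support that. Both sections name the next phase without cancelling scheduled visits; wording that sends a patient directly onward appears only in 13.9a and 13.9b. Section 13.2 likewise omits the end-of-maintenance visit, which the schedule plainly requires. The EOI column and footnote 1 are tied to the last induction dose, and an early stopper has one. The cycle 7 labels in 14.1 and 16.328 concern blood samples. What stands is an ambiguity: section 7.2 and those labels assume completed induction, and footnote 1 names two drugs jointly although Table 8.51 provides for stopping polatuzumab alone. Taking the later dose is the natural reading, but it is unstated.

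**On size.** A reader might take the 33% to 41% in section 1.231 as the share without a scan. It is discontinuation of polatuzumab for adverse events in earlier studies, not missing scans or stopping of all treatment. A reader might also infer that patients under 13.4 and 13.6 lose OS data. They do not: they stay in clinical and then survival follow-up, with PET on the same footnote 9 terms as other patients in post-treatment follow-up.

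**Conclusion.** The follow-up point holds. As written, 13.83 conflicts with 13.6, is out of step with 13.9a and 13.9b, and allows evaluable patients to lose later PFS and OS data. The size depends on how many are so judged, which is unknown; that the loss is related to outcome is plausible but not shown.

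The imaging point holds only as a clarification. The ordinary reading of the schedule gives an early stopper an EOI PET-CT, but other sections leave room for doubt. The power figures rest on an assumed unscanned share and on unscanned patients having the same 35% CR rate. Since 35% is the target among all evaluable patients, early stoppers included, the loss arises only if CRs occur and go unscanned. Its direction is conservative: the risk is abandoning an active regimen, not promoting an inactive one. The point merits an amendment but does not threaten the design.

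**What to change.** 1. Remove 13.83 from the 13.8 list. Route non-compliant patients by 13.6, or to survival follow-up under section 4.1 if they decline visits. Only withdrawal of consent for follow-up, or study or site closure, then ends follow-up. State the censoring rules for PFS and OS in 16.323 and 16.324 in the same amendment.
2. Reconcile footnote 1 with 7.2, 8.2, 13.4, 13.6, 14.1 and 16.328. State that the EOI PET-CT already in the schedule applies to patients who stop induction early without progression, 28 to 42 days after the later of the last induction rituximab or polatuzumab dose and before any new anti-lymphoma therapy, and that it counts as the EOI assessment.
3. State in 16.311 that an evaluable patient without an EOI assessment counts as non-CR.

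The cost is amendment wording and a few extra follow-up contacts. No new type of assessment is added, and neither treatment nor sample size changes.

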14.0 Body Fluid Biospecimens

14.1 Summary Table of Research Blood/Blood Products to Be Collected for This Protocol

Correlative Study	Mandatory or Optional	Blood or Body Fluid being Collected	Type of Collection Tube (color of tube top)	Volume to collect per tube (# of tubes to be collected)	Baseline (Drawn after registration but prior to cycle 1 treatment)	Day H	End of Induction Day 1 Cycle 7	End of Maintenance Day 1 Cycle 18		Temperature/
MRD	Optional	Blood	EDTA (purple)	10ml (1)	X		X	X		Ambient
Banking	Optional	Blood	EDTA (purple)	10ml (4)	X	X	X	X	X	Ambient
Banking	Optional	Blood	Streck CF DNA	10ml (2)	X	X	X	X	X	Ambient

 $^{^{1}}$ +/-8 weeks

After all samples have been processed according to kit instructions, ship all specimens according to shipping instructions (see Section 14.2 for detailed shipping instructions.)

14.2 Blood/Blood Products Handling

14.21 Kits are provided for this study.

The kit contains supplies and instructions for collecting, processing, and shipping specimens.

Participating institutions may obtain kits by e-mailing the Mayo Hematology Research Tissue Bank at E-mail requests should include the site address, contact information and number of kits being requested.

Kits will be sent via FedEx® Ground at no additional cost to the participating institutions. Allow 3 to 4 business days to receive the kits.

- 14.22 Label specimen tubes with the protocol number, the patient's initials (last, first, middle), study patient ID number (if available) and date of blood collection.
- 14.23 Collect all peripheral blood according to specific kit instructions (see table above).
- 14.24 Shipping

Specimens must be shipped the same day they are drawn.

Ship the EDTA and Streck whole blood tubes in the provided Styrofoam kits; no cold pack is required but may be used. The Fed Ex air bill is pre-addressed.

Ship specimens via Priority Overnight service on Monday – Thursday

(Friday only if you coordinate with lab contact) directly to:

Please send email message to The message should include the study name, sample type, Fed Ex air bill tracking number, contact name and telephone number. Phone calls if necessary, to

Shipping costs will be covered by the study if these kits and Fed Ex air bills are used for shipping specimens. Each kit contains the required tubes.

